## 7.3. Procedures for Recording Adverse Events

The side effects of interest will be collected through the completion of the daily diary only.

## 7.4. Reporting Procedures for Serious Adverse Events

Appendix E contains a flowchart summarising the procedure for SAE reporting. Healthcare professionals will report SAEs to the ARTIC PC coordination centre within 24 hours of becoming aware of the event. A medically qualified individual will be responsible for assessing the relatedness of the SAE to trial medication. All SAEs will be reported using the SAE form either on line or by paper and reporting this to the ARTIC PC coordinating centre. The ARTIC PC coordinator will maintain dedicated report lines with answerphone and fax facilities to allow reporting of SAEs. The answerphone and fax will be checked regularly during office hours.

The Chief Investigator (CI) or their designated representative will be responsible for assessing the expectedness of SAEs reported as being related to trial medication. Assessment of expectedness will

be based on the Summary of Product Characteristics. Reporting procedures for Suspected Unexpected Serious Adverse Reactions (SUSARs) are described in section 7.6.

The CI or designated PI at each clinical site will supply any supplementary information as requested by the MHRA, REC or ARTIC PC coordination centre.

## 7.5. Expectedness

Expectedness will be determined according to the Summary of Product Characteristics.

## 7.6. SUSAR Reporting

All SUSARs will be reported by the CI delegate to the relevant Competent Authority and to the REC and other parties as applicable. For fatal and life-threatening SUSARs, this will be done no later than 7 calendar days after the Sponsor or delegate is first aware of the reaction. Any additional relevant information will be reported within 8 calendar days of the initial report. All other SUSARs will be reported within 15 calendar days.

Principal Investigators will be informed of all SUSARs for the relevant IMP for all studies with the same Sponsor, whether or not the event occurred in the current study.

## 7.7. Safety Monitoring Committee

The trial Data and Safety Monitoring Committee will be responsible for reviewing SAEs after each recruitment season. The main aims of this review are as follows:

- To ensure the safety of each patient in the trial;
- To pick up any trends, such as increases in unexpected events, and take appropriate action;
- To seek additional advice or information from investigators where required;
- To evaluate the risk of the trial continuing and take appropriate action where necessary;
- To act or advise, through the Chairman or other consultant, on incidents occurring between meetings that require rapid assessment.

## 7.8. Development Safety Update Reports

In addition to the expedited reporting above, the CI shall submit once a year throughout the clinical trial, or on request, a safety report to the Competent Authority (MHRA in the UK), Ethics Committee, Host NHS Trust and Sponsor.

### 7.9 Criteria for the termination of trial

The DSMC will review SAEs after each recruitment season and discuss these with the Study/Trial Steering Committee (S/TSC). The Data and Safety Monitoring Committee, TSC or Sponsor may advise on whether the trial should be terminated.

## 8. HEALTH ECONOMICS

The primary economic analysis will be taken from a societal perspective but will also include the NHS and Personal Social Services (PSS) perspective. For NHS and PSS costs, we will collect data on medication, primary care visits, hospital stays, outpatient appointments and A&E attendances. All the information including adverse events will be collected through notes review forms at the end of the trial 28 days and CRFs. For the societal perspective, we will collect out-of-pocket spending, and time off work for parents taking care of children through a short questionnaire at the end of the study. All itemised resource usage will be weighted by their corresponding unit costs based on published sources (BNF, PSSRU and NHS reference costs).

We will measure the quality of life based on parents/cares proxy from EQ5DY, and the Visual analogue scale (VAS) used as part of the EQ5DY. The EQ5DY will be included as well as PedsQL™ (Pediatric Quality of Life Inventory™) on the basis that it measures quality of life at a point in time, and will be used in conjunction with the clinical outcome measures at days (1,7,14,21,28). This is important for an acute condition, and EQ5D was very helpfully used in the GRACE studies in adults to document change over time (and did change significantly which suggests it is likely to be useful in this population too). We will take this opportunity to investigate the associations between the different methods, which will help inform the use of proxy methods to measure children's' quality of life.

We will conduct an economic evaluation alongside the clinical trial. Accumulated costs and QALYs for each individual will be calculated based on an "area under the curve" approach. The cost-effectiveness analysis will be measured as costs per symptomatic day prevented and the incremental cost per quality adjusted life year gained (QALY). Generalized linear models will be employed to investigate the cost difference between interventions adjusted for baseline characteristics and bootstrapping methods will be used to produce incremental cost-effectiveness ratios and confidence ellipses. Cost-effectiveness acceptability curves will also be produced to reflect the probability of the intervention will be cost-effective at different given willingness to pay value per QALY gained. The cost effectiveness of antibiotics will be estimated in each subgroup.

Provisionally we propose not proceeding to long term modelling at this stage unless the intervention can be shown to be effective. For longer term modelling, particular attention will be given to including the benefits of reduced antibiotic use. Links will be made with work in progress in the Department of

Health on the societal value of reduced antibiotic resistance and with work by the Office of Health Economics on the incentives required for new antibiotic production.

## 9. STATISTICS

### 9.1. Description of Statistical Methods

The pilot data will examine organisational difficulties, fewer than expected eligible patients, discomfort about patients' eligibility and intervention efficacy, and patients' treatment preferences have been prominent issues in many trials, and have been recently described.(34) Unearthing the key problems for recruiters is of central importance in the piloting phase and we anticipate that the issues will become apparent, as they have in our previous studies, in the process of detailed and sensitive discussion/iteration between an experienced trial manager and the 20-30 recruiting clinicians who are likely to participate in piloting.

In addition Parents will be asked at 2 days and in the symptom diary into which trial arm they believe their child to have been randomised. We will calculate the proportion of parents who correctly guess the randomisation group at each time point. Assuming that parents have remained blind to allocation, we expect that this proportion will be no greater than might have been expected by chance (i.e. the 95% confidence interval will contain 50%).

Based on this we would then make any required adjustments to the recruitment procedures.

No interim analysis will be performed, and all analyses will be performed blind to group allocation using Stata version 13 (StataCorp). Subgroup analyses according to clinical signs and results of additional testing will be specified in advance and finalised blind to intervention group. Analysis of duration of symptoms will be performed using Cox proportional hazard models controlling for the severity of baseline symptoms with models controlling for any covariates. Kaplan Meier curves will be used to demonstrate the resolution of symptoms graphically. Analysis of symptom severity will use linear regression modelling, again controlling for the severity of baseline symptoms. Any evidence of a difference in benefit from antibiotics among the whole cohort will be assessed and also the key subgroups, and for each outcome also estimate an interaction term for each subgroup.

Our statistical analysis plan will be finalized after the internal pilot, prior to the main analysis being completed and by the Trial Steering Committee.

In addition the study team will explore to what extent results from additional tests (microbiological swabs, biomarkers, abnormalities on chest-X-rays, etc.) are potential effect modifiers, and differences between the purely observational data set and the trial data and our other large observational cohorts. (40, 41)

Since this data set will be one of the best characterised and most intensively investigated cohorts to date, a range of exploratory secondary analyses using logistic regression will provide additional useful

information: we will develop both diagnostic models (for bacterial infection, and for consolidation), and prognostic models (for children who have poorer outcome: non resolution of symptoms or the development of new symptoms or complications), and if appropriate develop clinical scores and estimate whether there is an interaction of such scores with treatment.

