The parents will keep a diary of symptoms and daily activities (including days away from work of parents) for at least one week and after that as long as symptoms persist up to four weeks after inclusion. All patients will be followed at 1 month when medication bottles will be returned and the symptoms diaries collected, and among willing participants over 6 years of age a forced-expiratory volume test will be done before and after administration of Salbutamol. This will allow some exploration of whether there is any difference in effectiveness among those with evidence of reversible airways obstruction. Parents/ guardians will be asked to guess individual treatment assignments (amoxicillin, placebo or don't know) and provide reasons for guesses on day 2 when as part of the telephone follow up before any evidence or side effects.

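### The 50% chance benchmark for blinding is also applied to a guess in the symptom diary, where blind parents can exceed it because the drug works; section 5.11 describes a day-2 guess only

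*Protocol*

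**What the plan says.** Protocol section 9.1 plans two guesses: "Parents will be asked at 2 days and in the symptom diary into which trial arm they believe their child to have been randomised". It continues: "We will calculate the proportion of parents who correctly guess the randomisation group at each time point". On the assumption that parents have stayed blind, "we expect that this proportion will be no greater than might have been expected by chance (i.e. the 95% confidence interval will contain 50" per cent). The stated use is "Based on this we would then make any required adjustments to the recruitment procedures", in a part of 9.1 that opens with what the pilot data will examine.

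Section 5.11 describes a single guess. Parents are asked to "guess individual treatment assignments (amoxicillin, placebo or don't know) and provide reasons for guesses on day 2", "as part of the telephone follow up before any evidence or side effects". It mentions no guess in the diary. It says the diary is kept "for at least one week and after that as long as symptoms persist up to four weeks after inclusion". Section 5.12 shows what the parent enters there: daily symptom scores, from which the primary outcome is derived, and diarrhoea, rash and nausea.

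**The concern.** The 50% figure is what one expects when guesses are unrelated to the arm. Blindness gives that only if nothing the parent can see differs between the arms. By the time of a diary entry, recovery and side effects may both differ. A parent who knows nothing of the allocation but reasons that a quick recovery or loose stools point to amoxicillin will be right more than half the time if amoxicillin speeds recovery or causes diarrhoea. At that point the benchmark mixes loss of blinding with efficacy and tolerability. Section 5.11 gives this as its reason for asking on day 2; section 9.1 adds a later guess without that safeguard.

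The primary outcome is rated by parents, so a blinding check that can fail for the wrong reason is worth correcting.

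**Working it through.** **Inputs from the protocol.**
- Pilot target 30 per group (60 in all), minimum 15 per group (section 5.9). This implies 1:1 allocation.
- 938 children at 80% follow-up (section 5.15): 938 × 0.8 ≈ 750 respondents.
- Answer options amoxicillin, placebo and *don't know* (section 5.11).
- Common amoxicillin side effects at 1% to under 10% (section 7).

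**Assumed, because the protocol does not give them:** the overall hazard ratio (HR), the fraction f of parents who guess from recovery, and the day of the diary guess.

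**Step 1: the stated 50%.** Let a and b be the probabilities of guessing amoxicillin in the amoxicillin and placebo arms. Then P(correct) = ½a + ½(1 − b). With a = b this is 50%, so the figure reproduces when every parent names an arm. The 95% interval around 50% is 37.3–62.7% at n = 60 and 46.4–53.6% at n = 750. By chance the interval lies wholly above 50% in about 2.6% of trials at either size (at least 38 of 60, or 402 of 750, correct).

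**Step 2: a diary guess, blinding intact.** A fraction f guesses amoxicillin if the child recovered faster than the pooled median; the rest guess at random. Let S₀ be the share of placebo children not yet recovered at that median. Under proportional hazards S₀ + S₀^HR = 1, and the difference in recovery is D = S₀ − S₀^HR = 2S₀ − 1. Then P(correct) = 0.5 + fD/2.
- HR 1.2: S₀ = 0.532, D = 0.063.
- HR 1.4: S₀ = 0.558, D = 0.116.

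Exact binomial probability that the 95% interval lies wholly above 50%:

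| HR | f | P(correct) | n = 750 | n = 60 |
|---|---|---|---|---|
| 1.0 | any | 50.0% | 2.6% | 2.6% |
| 1.2 | 0.25 | 50.8% | 6.6% | 3.4% |
| 1.2 | 0.5 | 51.6% | 14.2% | 4.5% |
| 1.2 | 1 | 53.2% | 41.8% | 7.3% |
| 1.4 | 0.25 | 51.5% | 12.7% | 4.3% |
| 1.4 | 0.5 | 52.9% | 36.5% | 6.7% |
| 1.4 | 1 | 55.8% | 89.5% | 14.8% |

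**Step 3: a second guessing model.** All parents are asked on a day when a fraction F of placebo children (30–70%) has recovered, and guess amoxicillin if their child has. Then D = (1 − F) − (1 − F)^HR.
- HR 1.2: 52.4–53.2% correct; interval above 50% in 27–44% of trials at n = 750 and 6–7% at n = 60.
- HR 1.4: 54.7–56.1% correct; 73–92% and 11–16%.

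**Step 4: side effects alone.** If guesses follow side effects only, with an assumed excess s of 1–10 percentage points on amoxicillin, P(correct) = 0.5 + s/2 = 50.5–55%. The interval lies above 50% in 5–79% of trials at n = 750 and 3–12% at n = 60.

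**Step 5: *don't know* kept in the denominator.** With a share d answering *don't know*, blind guessing gives (1 − d)/2 at any time point. At d = 0.2 this is 40%, interval 36.5–43.5% at n = 750, which misses 50% although nobody is unblinded. A real leak with 60% correct among those who guess shows as 0.6 × 0.8 = 48%, interval 44.4–51.6%, which passes.

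**The case against.** **Stage and consequence.** The check sits with the pilot text, is worded as an expectation, and leads only to adjusted recruitment procedures. At 60 children it would seldom be breached. This stands, and it limits the point. A reader might infer that a genuine benefit would be discounted as reporting bias; the protocol says nothing of the kind.

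**The hazard ratio of 1.7.** A reader might put 1.7 into Step 2 and obtain about 25, 71 and 99.9% at n = 750 for f = 0.25, 0.5 and 1. Section 5.15 defines 1.7 as the treatment interaction for the smallest subgroup, not as an overall effect. With 1.7 in 30% of children and 1.0 in the rest, the same model gives about 6, 12 and 36%. The protocol gives no overall hazard ratio, so 1.2 and 1.4 are illustrations.

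**Timing.** The available text does not state the day of the diary guess, and the contents of the follow-up table in Appendix D could not be read. That effects are visible by then is a strong inference from a diary of one to four weeks, not a stated fact.

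**Day 2 as the only valid test.** This is too strong. Section 5.12 names days 2–4 as when antibiotics might make a difference, so day 2 is the least contaminated time, not a pure one.

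***Don't know* answers.** Kept in the denominator, they push the proportion down and can hide the effect shown here. With 10% *don't know* and an overall hazard ratio of 1.7, the rates at n = 750 fall to about 0, 1 and 43%. This stands: the direction of error depends on a denominator that section 9.1 does not settle.

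**Left to the SAP.** The choice of blinding index can wait for the SAP. The time points and the benchmark cannot be treated as left open, because section 9.1 already fixes them.

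**Conclusion.** The point holds in a limited form. Section 9.1 applies to the diary guess a benchmark that does not test blinding there, and it disagrees with section 5.11 on when guesses are taken.

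If every parent names an arm, an overall hazard ratio of 1.2 to 1.4 would put the interval wholly above 50%, with blinding intact, in about 7 to 90% of trials at 750 respondents, depending on how many parents guess from recovery. At the pilot target of 60, the only stage for which the text states a use, the range is about 3 to 15%, against 2.6% by chance. The sizes rest on assumed hazard ratios and guessing behaviour. The direction rests only on parents using what they see.

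Severity is minor. The primary efficacy analysis is unaffected.

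**What to change.** 1. Reconcile sections 5.11 and 9.1: state whether a diary guess is taken and, if so, on which day.
2. In section 9.1, apply the 50% benchmark to the day-2 telephone guess only, described as the least contaminated check available. Compute it among parents who name an arm, or use a blinding index that handles *don't know*, and report the *don't know* share by arm.
3. Report any diary guess descriptively by arm, with reasons where they are collected, and state that it is not read as a test of blinding.

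**Cost.** A few sentences and no new data. Section 5.11 describes reasons for the day-2 guess only, so reasons in the diary would need an added item if wanted. The diary guess no longer feeds a formal check. Restricting to parents who name an arm loses some precision: with an assumed 20% *don't know*, 60 becomes 48 and the half-width of the interval at 50% rises from 12.7 points to 1.96 × √(0.25/48) = 14.1 points.

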## 5.9. Pilot phase

As agreed with the funder, an internal pilot phase will be carried out to assess the feasibility of this trial during the initial 6-7 months of the study. This will only involve the lead centre (Southampton) and between 5 and 10 GP practices and or Hospitals each recruiting between 6 and 8 patients. For the pilot phase, the target is to recruit 30 participants in each group with a minimum of 15 participants in each.

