## 5.15. Sample size calculation

Pilot phase: there is no sample size calculation.

Main phase: An alpha of 0.01 is chosen to allow for 5 pre-specified subgroups, which occur in at least 30% of children based on our previous data (sputum (65%), fever (64%); generally unwell rated as a bad problem (30%); short of breath (36%) abnormal chest signs (crepitations: 43% ). Previous consensus documented less than 2-3 days difference in symptoms rated moderately bad or worse is unlikely to be a sufficient reason to prescribe antibiotics, and 3 days should probably now be the minimum given the short and long term disadvantages of antibiotics, (9, 10) and in particular increased national and international concern over the danger of antibiotic resistance (<https://www.gov.uk/government/publications/resources-to-support-the-2012-european-antibiotic-awareness-day-in-england>; <https://www.gov.uk/government/news/prime-minister-warns-of-global-threat-of-antibiotic-resistance> ). (3, 4) To detect a hazard ratio for the treatment interaction of 1.7 (see Appendix 2 to this protocol: equivalent to 3 days difference between a subgroup and the whole sample), for the smallest subgroup of interest (30% of the sample), using the equations of Schmoor et al requires 738 individuals for 80% power and 938 individuals for 90% power (assuming 80% follow-up). (36) The other (larger subgroups) will have greater power. To allow for some leeway in our assumptions we will aim to recruit at least 1000 children.

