## DISPENSING

A unique medication number will be printed on each pack of IMP which corresponds to one of the 2 treatment arms. Investigator staff will randomise and dispense by selecting the next sequentially numbered IMP pack.

IMPs are to be dispensed only in accordance with the protocol.

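### Section 9.1 tests the day 2 treatment guess against 50% correct although parents may answer don't know; with those answers in the denominator, as worded, the benchmark is too lenient

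*Protocol*

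**What the plan says.** Section 5.11 of the protocol describes the day 2 telephone question. Parents are asked to "guess individual treatment assignments (amoxicillin, placebo or don't know"), so there are three possible answers.

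Section 9.1 adds a second time point: "Parents will be asked at 2 days and in the symptom diary into which trial arm they believe their child to have been randomised". The answer options in the diary are not given.

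The statistic is fixed in section 9.1: "We will calculate the proportion of parents who correctly guess the randomisation group at each time point". The standard follows, in per cent: "we expect that this proportion will be no greater than might have been expected by chance (i.e. the 95% confidence interval will contain 50". Section 9.1 then says that recruitment procedures would be adjusted as needed on this basis.

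There are two arms: each pack carries a number "which corresponds to one of the 2 treatment arms" (section 6.1, Dispensing). Nowhere does the protocol remove don't-know answers from the denominator or lower the 50% to allow for them.

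**The concern.** A question with three answers is judged against the chance rate of a question with two. A parent who says don't know is never correct, so each such answer pulls the overall percent correct down. Parents who do name a treatment can then be right well above chance while the overall figure stays near 50%, and the rule reads this as blinding kept.

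The same mismatch makes the standard disagree with itself. A truly blind group with some don't-knows will often have an interval wholly below 50%. That satisfies the first half of the sentence (not above chance) but not the explanation in brackets (the interval contains 50%).

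Parents complete the diary that yields the primary outcome (section 5.12), so whether they can tell the arms apart matters. A check that can miss this gives false comfort.

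**Working it through.** **Inputs.**
- Three answers at day 2 (section 5.11); two arms (section 6.1, Dispensing).
- Pilot: "the target is to recruit 30 participants in each group with a minimum of 15 participants in each" (section 5.9), so 60 answers at target if all parents reply. Equal groups suggest 1:1 allocation. No ratio is stated, so 1:1 is an assumption.
- Main trial: "we will aim to recruit at least 1000 children" (section 5.15). With the 80% follow-up assumed there, 0.8 × 1000 = 800 answers. That this share applies to the guess, and that the rule is applied again at full size, are assumptions.
- The don't-know share d is not given. A range of 10% to 50% is assumed, equal in both arms.

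**Reproducing the 50%.** Suppose every parent names an arm, a share a says amoxicillin, and guesses are unrelated to allocation. Then P(correct) = 0.5a + 0.5(1-a) = 0.50 for any a. The protocol's figure is right if there are no don't-knows or they are left out.

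**With don't-knows in the denominator.** Chance is (1-d)/2. An overall 50% correct corresponds to 0.5/(1-d) correct among those who guessed.

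| d | Chance, all parents | Share of guessers right when 50% of all parents are correct |
|---|---|---|
| 10% | 45% | 56% |
| 20% | 40% | 62.5% |
| 30% | 35% | 71% |
| 40% | 30% | 83% |
| 50% | 25% | 100% |

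**How often an unblinded group passes.** The 95% Wilson interval contains 50% when 23 to 37 of 60, or 373 to 427 of 800, are correct. If a share q of guessers is right, the overall probability correct is q(1-d). Exact binomial sums over those ranges give:

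| n | d | q | q(1-d) | P(interval contains 50%) |
|---|---|---|---|---|
| 60 | 0 | 75% | 0.75 | 0.015 |
| 60 | 30% | 75% | 0.525 | 0.93 |
| 60 | 0 | 80% | 0.80 | 0.001 |
| 60 | 20% | 80% | 0.64 | 0.40 |
| 60 | 30% | 80% | 0.56 | 0.84 |
| 60 | 40% | 80% | 0.48 | 0.94 |
| 800 | 20% | 62.5% | 0.50 | 0.95 |
| 800 | 30% | 75% | 0.525 | 0.70 |
| 800 | 30% | 80% | 0.56 | 0.07 |
| 800 | 40% | 80% | 0.48 | 0.79 |

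The 62.5% row has an overall rate of exactly 50%, so about 95% follows by construction. It shows that moderate unblinding passes at full size. With Clopper-Pearson intervals at n = 60 and q = 75%, the figures are 0.96 at d = 30% and 0.03 at d = 0.

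**How often a blind group's interval contains 50%.** At n = 60: 0.65, 0.34 and 0.10 for d = 20%, 30% and 40%. At n = 800: 0.19 for d = 10% and below 0.001 for d = 20%. Almost all the other intervals lie wholly below 50%.

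**Effect of leaving don't-knows out.** At n = 60 and d = 30%, 0.7 × 60 = 42 parents name a treatment. The interval contains 50% for 15 to 27 correct of 42. With 75% of guessers right this has probability 0.08, against 0.93 under the present wording. With blind guessing it is 0.96.

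**The case against.** **Don't know is not a guess, so the stated 50% may itself imply that only parents who named an arm are counted.** That reading makes the benchmark correct. It may be what the team intends, and the analysis plan could say so. But the sentence counts a proportion of parents and is silent on exclusions. The protocol has already fixed the statistic, the reference value and the criterion, so this is more than a detail left for later. Followed literally, it gives the wrong answer.

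**A reader might infer that the rule rejects blind trials.** The text does not support that in full. An interval wholly below 50% still meets the first half of the sentence and fails only the explanation in brackets. What stands is that the two halves disagree. Relying on the first half alone does not cure the leniency: with 80% of guessers right, the interval is not wholly above 50% with probability 0.845 at n = 60, d = 30%, and 0.999 at n = 800, d = 40%.

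**A reader might infer that a grossly unblinded full-size trial would usually pass.** That depends on d. With 80% of guessers right at n = 800, it takes a don't-know share of about 40%; at 30% the rule detects the problem more than nine times in ten.

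**The check has limited consequences.** Blinding rests on matching placebo, identical bottles, numbered packs and codes held away from sites (sections 5.8 and 6.1). The only stated use of the guess is to adjust recruitment procedures. This stands, and it limits the weight of the point.

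**Conclusion.** The point holds for the day 2 question. Section 9.1 applies a two-answer chance value to a three-answer question and, as worded, keeps don't-knows in the denominator. The benchmark is then too high by 0.50 - (1-d)/2 = d/2, for example 15 percentage points at d = 30%, and a larger sample does not remove this.

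The practical effect is clearest at pilot size, where a don't-know share of 20% to 30% is enough to hide substantial unblinding. At main-trial size the rule lets moderate unblinding through, and gross unblinding only when don't-knows are common.

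These sizes rest on an assumed d, 1:1 allocation, an equal don't-know share in both arms, and, for the larger n, use of the rule beyond the pilot. The point does not extend to the diary question, whose options are unstated. It does not show that blinding failed or that the primary efficacy estimate is biased; it concerns only the check.

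**What to change.** In section 9.1, and in the analysis plan to match:
- compute percent correct with its 95% confidence interval only among parents who named a treatment, with 50% as the reference;
- report the don't-know share by arm, since a difference between arms would itself be informative;
- make the two halves of the criterion agree, for example by saying whether an interval wholly below 50% meets it;
- state the answer options for the diary question, so that the same rule can be applied there.

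A blinding index that takes three responses, such as James's, or Bang's by arm, may be added but is not needed. If Bang's index is used, note that a blind group leaning to one answer gives non-zero values of opposite sign in the two arms.

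The cost is a sentence or two of text. No new data are needed and no efficacy analysis changes.
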